3.1 Risks to human subjects

a. Human subjects involvement, characteristics, and design

Volunteers who are eligible and willing to participate will undergo the intervention protocol and procedures described in the Research Plan. We plan to enroll 66 volunteers in the study. They will be healthy, eumenorrheic premenopausal women, aged 40 to 60 years. Eumenorrheic premenopausal status is defined as not yet reaching the Early Menopausal Transition Stage -2 by the Stages of Reproductive Aging Workshop (STRAW) criteria.⁹⁹ Stage -2 is characterized by a change in cycle length of 7 or more days (e.g., regular cycles every 24 days instead of 31 days). Accordingly, the medical history will query for cycle regularity in the past year and whether cycle length has changed. The investigators debated whether to have an exclusion criterion for participation in regular exercise. In the absence of knowledge as to whether women who exercise

regularly may be more or less susceptible to the potential effects of gonadal function to regulate physical activity, it was decided that this should not be too restrictive. Thus, only women who exercise at least 30 minutes per day at a moderate to vigorous intensity most days of the week (defined as >4 d/wk) will be excluded. The prospective cohort study that supports a decline in PAEE during the menopausal transition did not have an eligibility criterion based on physical activity level.¹² The investigators also debated whether there should be an exclusion criterion for body mass index (BMI). The prospective cohort study did not have one.¹² That paper did not report BMI, but fat mass averaged ~40% of body weight. In our experience, that falls into the 'obese' category by BMI. Based on this, we chose the exclusion threshold as a BMI $\geq 40 \text{ kg/m}^2$.

Inclusion criteria

Volunteers will be women aged 40 to 60 years who are still experiencing regular menstrual cycles. They must be willing to be randomized to placebo or GnRH_{AG} therapy for 24 weeks. They must be physically able and willing to be randomized to participate in a supervised exercise training program. Volunteers for the Vascular sub-study will be recruited from the larger group of participants in the parent study.

Exclusion criteria

Volunteers will be excluded from participation for the following:

- irregular menstrual cycles defined as 2 or more missed cycles in the previous year
- serum FSH >25 mIU/mL measured during the first 5 days of the menstrual cycle
- on hormonal contraceptive or menopausal therapy
- positive pregnancy test
- intention to become pregnant or start hormonal contraceptive therapy during the period of study
- lactation
- known hypersensitivity to GnRH or leuprolide acetate
- CES-D score ≤ 16 OR CES-D score >16 with clinician follow-up and BDI-II score <18
- severe osteopenia or osteoporosis (i.e., proximal femur or lumbar spine t scores < -2.0)
- abnormal vaginal bleeding
- thyroid dysfunction, defined as an ultrasensitive TSH <0.5 or >5.0 mU/L; volunteers with abnormal TSH values will be re-considered for participation in the study after follow-up evaluation by the PCP with initiation or adjustment of thyroid hormone replacement
- uncontrolled hypertension defined as resting systolic BP >150 mmHg or diastolic BP >90 mmHg; participants who do not meet these criteria at first screening will be re-evaluated, including after follow-up evaluation by the PCP with initiation or adjustment of anti-hypertensive medications
- cardiovascular disease; subjective or objective indicators of ischemic heart disease (e.g., angina, ST segment depression) or serious arrhythmias at rest or during the graded exercise test (GXT) without follow-up evaluation; follow-up evaluation must include diagnostic testing (e.g., thallium stress test) with interpretation by a cardiologist
- history of venous thromboembolic event
- orthopedic or other problems that would interfere with participation in the exercise program
- BMI $\leq 40 \text{ kg/m}^2$

The proposed studies do not involve special classes of subjects that may be considered vulnerable populations. There are no additional exclusion criteria for the Vascular sub-study

Study group assignment

The approach by which eligible volunteers will be randomly assigned to a study group is described in section 2.d.6.

Justification for dose and frequency of study drug administration

The rationale for the study drug regimen is discussed in section 2.d.7.

b. Sources of materials

The research materials that will be collected from human subjects include:

- medical records – only when needed to follow-up on health status
- blood and tissue samples – for screening and for study-specific outcomes, as described in the research strategy
- data – from all the study procedures, as described in the research strategy

Only members of the research team will have access to protected health information (PHI) collected from the volunteers. Confidentiality of electronic data will be maintained by using only patient identification numbers for data entry. Samples sent to collaborators within the institution (Drs. [name] and [name]) will be de-identified. The master document linking patient names with identification numbers will be maintained in a separate password-protected file with restricted access. Paper records will be kept in individual study charts that are stored either in a locked cabinet or in a locked office. Data records will be maintained for at least 7 years after the publication of results. At that time, the data records may be destroyed by the PI by deleting them from electronic media and by shredding paper documents, but some of the data records may be retained indefinitely.

Sharing of data among investigators within the institution is typically facilitated either by providing a password for the database or by electronic transmissions. All members of the research group have individual computers that are part of the institution network with institutional oversight of security. Files that contain data that could jeopardize blinding to treatment code are password-protected to restrict access. Sharing of data with investigators or monitoring personnel outside the institution is typically facilitated by electronic transfer, in a manner that is compliant with HIPAA regulations.

c. Potential risks

Study drugs: All participants will be randomized to receive placebo (saline) or GnRH_{AG} (leuprolide acetate) 3.75 mg/mo by intramuscular injection every 4 weeks for 24 weeks (6 doses).

leuprolide acetate

Contraindications for use include: hypersensitivity to GnRH, GnRH agonist analogs or any of the excipients in Lupron Depot; undiagnosed vaginal bleeding; known or suspected pregnancy; lactation.

In women who are pregnant, use of leuprolide acetate may cause fetal abnormalities.

Leuprolide acetate may cause an anaphylactic reaction in volunteers with hypersensitivity to GnRH.

Convulsions have been observed in patients taking leuprolide acetate. These included patients with medical conditions or those taking medications associated with convulsions. Convulsions have also been reported in patients without any of these conditions.

Regular menstruation should stop during leuprolide acetate therapy but spotting or breakthrough bleeding may occur. Cessation of menses does not ensure that pregnancy will not occur. Normal menstrual function is usually restored within 2-3 months after therapy is discontinued.

Leuprolide acetate may cause symptoms related to hypoestrogenism including hot flashes, headaches, nausea, emotional lability, decreased libido, acne, myalgia, sleep disorder, reduction in breast size, and vaginal dryness. Bone loss may occur, although the amount lost over the 24-week intervention should not be clinically significant and should be recovered slowly after discontinuation of leuprolide acetate treatment. There may be a development or worsening of depression and the occurrence of memory disorders.

Leuprolide acetate therapy for 24 weeks may cause an increase in fat mass (1-2 kg), a decrease in fat-free

mass (1-1.5 kg), an increase in total, LDL, and HDL cholesterol (5-10%), and an increase in triglycerides (15-20%).

Local injection site reactions including induration and abscess may occur.

Tissue biopsies: The risks associated with adipose tissue and muscle biopsies include brief, mild burning pain from the local anesthetic (lidocaine), more than mild discomfort during the acquisition of muscle tissue (about 10% of cases), and infection (less than 0.4% of cases). Allergy to the anesthetic (skin swelling or rash) occurs rarely. There may be persistent numbness in the biopsy area, but this is rare.

DXA: The DXA (to assess BMD and body composition) procedure involves exposure to ionizing radiation. All DXA measurements during the study (whole body 3 times, lumbar spine and proximal femur 2 times) during the study involve a total effective radiation exposure that is roughly equivalent to spending 5 days outside in Denver (<50 mrems), or about ~1% of the annual allowable exposure for radiation workers. This risk is minimized by having trained technicians conduct the DXA scans, thereby reducing the likelihood of needing repeat assessments.

Exercise Testing and Training: The risks associated with exercise include falls, pain in muscles or joints, dizziness, fainting, irregular heartbeats. Rarely, exercise testing can result in a stroke, heart attack, or death. The risk of death during or immediately after an exercise test is less than 1 in 10,000. The risk of a heart attack during or immediately after an exercise test is less than 4 in 10,000. The risk of a problem that would require hospitalization, such as chest pain, is less than 2 in 1000. The same discomforts and risks are present during the exercise training program.

Venipuncture and IV catheters: There is a small risk of local hematoma, infection, and thrombosis associated with intravenous blood sampling.

Arterial endothelial function test (Vascular sub-study): the 5 minutes of cuff occlusion may cause a tingling in your fingers and hands, a feeling of pins and needles, and may cause you to feel pain.

Confidentiality and privacy: The use of questionnaires, interviews, and collection of personal medical information poses a risk to confidentiality and privacy and may cause embarrassment.

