Other secondary outcomes of the study will include: 24-h TEE measured by DLW; REE, SEE, and TEF measured by indirect calorimetry in a metabolic chamber; energy intake estimated from food records; physical activity measured by accelerometry; body composition measured by dual-energy x-ray absorptiometry (DXA); glucose and insulin responses to an OGTT; serum concentrations of inflammatory cytokines (IL-6, hsCRP); and biomarkers in adipose tissue samples.

2.d.3. Study population

Volunteers will be women nearing the menopausal transition, based on age (40 to 60 y), with normal menstrual cycle function. The **rationale** for this approach was driven by the observation that a menopause-related decline in PA likely begins 3 to 4 years before menopause (Fig 6). We chose not to focus the study on women with perimenopausal symptoms for two reasons: 1) we may miss part of the perimenopause-related change in PAEE, and 2) the irregularity of menstrual cycles during the perimenopause complicates the scheduling of baseline tests around menstrual cycle phase. Specific inclusion and exclusion criteria are in Section 3.1.a.

2.d.4. Sample size justification

The expected effect of ovarian hormone suppression on PAEE was conservatively set at -25%, based on the range of decreases in physical activity observed in preclinical studies of -30% to -80% (Fig 1) and the decrease

of -50% in the prospective cohort study of women undergoing natural menopause.¹² Baseline PAEE was assumed to be 800 kcal with a SD of 330 kcal.⁶⁵ The variance of the difference between PAEE_{pre} and PAEE_{post} is $2(1-\rho)\sigma^2$. Using a conservative value of 0.90 for ρ (actual value, 0.98)⁶² and assuming no change in variance as PAEE decreases, the SD of the change will be 148 kcal/d. Based on the analysis plan to conduct a 1-way ANOVA with two contrasts (placebo vs GnRH_{AG}; GnRH_{AG} vs GnRH_{AG}+exercise), a sample size of 15 in each of 3 groups will achieve 95% power for either test to detect a 200 kcal/d difference between two groups in the change in PAEE using a *t* test at the 0.05 significance level. To account for attrition, we will enroll 22 per group.

2.d.5. Screening procedures

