After providing informed consent, volunteers will undergo 2 days of screening tests. Day 1 will include an assessment of depressive symptoms (Center for Epidemiologic Studies Depression Scale (CESD), a clinical laboratory evaluation including a comprehensive metabolic profile, TSH, a complete blood count, and a medical history and physical examination by the study clinician. If volunteers are found to be depressed after administering the CESD (score of >16), the study clinician will administer the Beck Depression Inventory (BDI-II). As score of <18 on the BDI-II will be used along with clinical judgement to determine final eligibility; this approach was used in a previous study completed by [name]. At the second visit, participants will undergo proximal femur and lumbar spine DXA scans to exclude volunteers who have severe low bone mass or osteoporosis (BMD t-scores of <-2.0) because BMD may decrease during GnRH_{AG} treatment. A urine pregnancy test will be done prior to the DXA scan. Afterwards a resting BP and 12-lead ECG will be recorded and then a graded exercise test (GXT), with monitoring of BP and 12-lead ECG, will be administered by research personnel and supervised by a clinician. After screening tests are completed, an enrollment checklist that includes all enrollment criteria will be completed for each volunteer and reviewed by a study clinician and another investigator to verify eligibility.

2.d.6. Randomization and blinding

Volunteers will be informed that they will be randomized to placebo or active GnRH_{AG} and to exercise or no exercise. They will *not* be informed that only women on active GnRH_{AG} will be randomized to exercise. A permuted block randomization with random block sizes will be used for subject assignment into the 3 treatment groups. Randomization will be stratified by age (40-46, 47-60 y). The randomization sequences will be generated by the biostatistician, who will determine the treatment assignment for an individual once study eligibility has been confirmed. The treatment assignment will be given to the research nurse, who will oversee the administration of the placebo (saline) and GnRH_{AG} injections. The nurse will not be responsible for acquisition of study outcomes data; such data will be collected by research staff members who are blinded to drug status. Randomization will occur after eligibility for the study has been determined.

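### The Section 3.1.a exclusion list reverses the depression and BMI rules stated elsewhere in the protocol; as printed, the two versions admit no woman in common

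*Combined protocol and SAP*

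**What the plan says.** Section 2.d.3 states: "Specific inclusion and exclusion criteria are in Section 3.1.a". Within Section 3.1.a the bullets stand under the heading "Volunteers will be excluded from participation for the following". Two of them matter here:

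- Depression: "CES-D score ≤ 16 OR CES-D score >16 with clinician follow-up and BDI-II score <18".
- BMI: 40 kg/m² or below.

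Two other places give the same rules. Section 2.d.5 takes a CES-D above 16 as the depressed result that leads to the BDI-II, and continues: "As score of <18 on the BDI-II will be used along with clinical judgement to determine final eligibility". The narrative of Section 3.1.a, after explaining the choice, says "Based on this, we chose the exclusion threshold as a BMI" of 40 kg/m² or more.

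For how the criteria are applied, Section 2.d.5 says that "an enrollment checklist that includes all enrollment criteria will be completed for each volunteer", with review by a study clinician and a second investigator.

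**The concern.** Under an exclusion heading, each bullet should describe a woman who may not enter. The depression bullet instead describes a woman who passes the screen in Section 2.d.5, and the BMI bullet covers the range that the narrative allows. A person who builds or audits the checklist from the list alone would turn away every woman who passes the depression screen.

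The depression item matters most because it is a safety screen. On leuprolide, Section 3.1.c warns: "There may be a development or worsening of depression and the occurrence of memory disorders". Two of the three arms receive the drug, so 2 × 22 = 44 of the 66 planned participants would be exposed. The double review of the checklist does not settle the matter, because the protocol does not say which version of a contradictory rule the checklist carries.

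**Working it through.** The plan gives no figure to reproduce here. The check is one of eligibility logic.

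**Side by side**

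| Item | List in 3.1.a, read literally | Section 2.d.5 and 3.1.a narrative |
|---|---|---|
| CES-D ≤16 | excluded | passes, no further step |
| CES-D >16, BDI-II <18 after clinician follow-up | excluded | may be eligible, with clinical judgement |
| CES-D >16, BDI-II ≥18 | not excluded | does not meet the stated BDI-II score |
| BMI <40 | excluded | not excluded |
| BMI =40 | excluded | excluded |
| BMI >40 | not excluded | excluded |

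The heading cannot be reread as an inclusion heading. Neighbouring bullets, such as FSH above 25 mIU/mL, t scores below -2.0 and a positive pregnancy test, are genuine exclusions.

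**Counting combinations.** Three depression results by three BMI results give 3 × 3 = 9. The count assumes that every woman with a CES-D above 16 gets the clinician follow-up described in Section 2.d.5.

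| Reading | List admits | Narrative admits | Shared |
|---|---|---|---|
| As printed, BDI-II <18 required | 1 (BDI-II ≥18, BMI >40) | 2 (either passing result, BMI <40) | 0 |
| List's BMI sign taken as ≥ | 1 (BDI-II ≥18, BMI <40) | 2 | 0 |
| Only the depression bullet reversed | 2 (either passing result, BMI >40) | 2 | 0 |
| As printed, but judgement may admit BDI-II ≥18 | 1 | 3 | 0 |
| BMI sign taken as ≥ and judgement may admit BDI-II ≥18 | 1 | 3 | 1 |

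**Finer grid.** The same rules were run over CES-D 0 to 60, BDI-II 0 to 63, BMI 15 to 60 in steps of 0.5, and follow-up yes or no. The ranges are assumptions. This gives 61 × 64 × 91 × 2 = 710,528 profiles.

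- List: 44 CES-D values × (46 × 2 + 18 × 1) BDI-II and follow-up pairs × 40 BMI values = 193,600 admitted. The 18 × 1 term is the woman above the CES-D cut-off with no clinician follow-up, whom the literal bullet does not exclude.
- Narrative, BDI-II <18 required: (17 × 64 × 2 + 44 × 18) × 50 = 148,400 admitted.
- Admitted by both: 0. If judgement may admit a BDI-II of 18 or more, the narrative admits 249,600 and the joint overlap is still 0 because of BMI.

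**Could the depression bullet be a misread sign?** If its first comparison is read as ≥16, the bullet still excludes a woman with CES-D 20 and BDI-II 10, whom Section 2.d.5 treats as potentially eligible. One changed sign does not repair it.

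**Lesser, editorial points.** The Stage -2 example in Section 3.1.a (31-day cycles becoming 24-day, a change of 7 days) goes from 365/31 = 11.8 to 365/24 = 15.2 cycles a year with none missed, so it passes the missed-cycles bullet. The exclusion for regular exercise (3.1.a narrative) and that for local-anaesthetic allergy (3.2.b) are absent from the bullets.

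**The case against.** The strongest reply is that this is a drafting slip with the intent visible nearby. Section 2.d.5 sets out the depression screen step by step, the 3.1.a narrative gives the BMI threshold with its reasoning, and the population is described as healthy women, so nobody would sensibly enrol only screen failures with a BMI above 40. What is applied to each volunteer is the checklist, whose text we do not have. That limits the likely harm. It does not make the list correct, because Section 2.d.3 names the section that contains it as the source of the criteria.

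Second, the BMI conflict turns on one sign that may have been misread from the PDF. This stands as a caution: the bullet should be compared with the source file. Without the BMI conflict, zero overlap rests on the depression rules and needs a BDI-II below 18 to be a firm requirement, which the reference to clinical judgement leaves open.

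Third, counting cells measures no effect on power or bias. That is right, and none is claimed.

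Fourth, the cycle, exercise and allergy rules are all in the protocol and apply together, so their absence from the bullets is a matter of placement. That is also right; they carry no weight in the conclusion.

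**Conclusion.** The concern holds. The depression bullet states a passing result as a reason for exclusion, and no other passage corrects it. As printed, the BMI bullet also contradicts the narrative in its own section. The list and the narrative rules have no eligible woman in common, whichever way clinical judgement is read. If the BMI sign is a reading slip, that still follows provided judgement does not admit a woman with a BDI-II of 18 or more. Without that proviso the two overlap only in women with such a score, and the list still excludes every woman who passes the screen.

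This should be corrected, because a safety criterion is inverted in the section that the protocol names for eligibility. No analysis or sample-size figure depends on it, and the documents give no sign of wrongful enrolment.

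**What to change.** - Reconcile Section 2.d.5 with the narrative and list in Section 3.1.a, so that the depression and BMI rules are each stated once, in the direction the sponsor intends. Keep the role of clinical judgement explicit, including whether it can override the BDI-II score.
- Compare the BMI sign with the source PDF.
- Bring the cycle-length, exercise and anaesthetic-allergy rules into the list, or cross-reference them.
- Confirm that the enrolment checklist carries the reconciled wording.

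The thresholds are for the sponsor and clinicians to confirm; none is proposed here. The cost is a protocol wording correction and one reading of the checklist.

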3.2 Adequacy of protection against risks

a. Recruitment and informed consent

Volunteer recruitment

Recruitment of volunteers for the study will rely on strategies that have proven successful in attracting volunteers to other projects the PI has conducted, including projects involving GnRH_{AG} and exercise interventions. The recruitment strategies will include (ranked from most to least successful):

- radio advertisements – utilization of radio stations that target a demographic consistent with the study population
- direct mailings – fliers sent to households meeting specified demographics in geographics regions proximal to UCAMC
- e-mail bulletins – system-wide (e.g., UCAMC and UCH) e-mail blasts
- suburban newspaper advertisements – there are many suburban journals in the Metro area that are issued on a weekly or monthly basis; we specifically advertise in those that target neighborhoods in relative proximity to UCAMC and those that target persons from under-represented minority groups
- major newspaper advertisements – the major publication in the Denver Metropolitan area has a Health and Fitness section that runs once per week; advertisements in these sections have targeted appropriate individuals for our previous studies
- study pamphlets – pamphlets describing the study will be printed for a variety of purposes (for study participants to give to family and friends who may be interested in participating; to place in the UCAMC Ob/Gyn Clinic and other relevant clinics; to place in community recreation centers; to hand out when

the investigators give community lectures)

- university advertisements – advertisements will be placed on a quarterly basis in the two UCAMC publications that target students/faculty/staff and alumni
- community lectures – the investigators participate in a UCAMC-sponsored health-related lecture series for the community as well as other lectures sponsored by local churches and organizations

Informed consent process

The consenting process is part of the first orientation session, which takes 60-90 min. Volunteers are either sent a copy of the consent form in advance or are given one at the start of the orientation; time is allowed for review of the consent form. Volunteers then meet with a member of the research team to a) have the study and what is expected of them explained in detail; b) discuss their reasons and motivation for wanting to participate to determine whether they are realistic; c) discuss any practical problems (e.g., scheduling conflicts, vacations) that could interfere with participation; d) have their questions answered; and e) demonstrate their ability to provide informed consent by describing their understanding of the major study goals and what is expected of them if they choose to participate. The research team member in charge of informed consent will fill out the documentation of informed consent standard checklist. Volunteers are given a signed copy of the consent form and a signed copy of the consent and the documentation of informed consent checklist will be maintained in the study chart for each participant. The consent form includes HIPAA authorization.

Members of the research group who obtain consent and HIPAA authorization will be in compliance with IRB and HIPAA education requirements. The PI will have the responsibility of ensuring that research personnel are prepared to convey study information to volunteers.

b. Protections against risk

Plans to minimize risks

Study drugs: The risks associated with use of the study drugs will be minimized by enrolling participants who do not have contraindications for their use. Volunteers will undergo a medical history and physical examination by the study clinician and will undergo a maximal exercise stress test. Participants will be observed for 30 min after drug injection to monitor for new hypersensitivity reactions. Absence of pregnancy will be confirmed before placebo or GnRH_{AG} are administered. Women will be instructed that they should not become pregnant while taking study drugs because of risks to the fetus. They will be instructed that cessation of menses may or may not occur during the study and that cessation of menses does not provide protection against pregnancy; contraception (not hormonal) must be used. The exercise training intervention that one-third of the participants will engage in is expected to minimize changes in body composition. Participants randomized to the non-exercise arms will be given the opportunity to undergo exercise training after the study to help reverse any changes in body composition that occurred.

DXA: The risk of radiation exposure is minimized by having trained technicians administer the procedures, thereby reducing the likelihood of needing repeat assessments. Pregnancy tests will be done prior to each DXA scan to reduce risk of fetal radiation exposure.

Exercise testing and training: The risks of exercise testing and training will be minimized by adhering to the following strategies:

Endpoints for exercise tests: In asymptomatic individuals who do not develop cardiovascular abnormalities, the endpoint for the maximal exercise tests will be severe fatigue that forces cessation of exercise. The criteria that will be used to stop the exercise test before volitional fatigue include the development of: (a) ST-segment depression of more than 0.2 mV that is either horizontal, downsloping, or slowly upsloping (less than 1 mV/sec) and lasts for 0.08 sec, or ST-segment elevation greater than 0.1 mV; (b) chest pain or discomfort; (c) serious arrhythmias, including multifocal PVCs, ventricular tachycardia, frequent (>10/min) PVCs or couplets, or sustained atrial tachyarrhythmias; (d) A-V block or other conduction defects; (e) a fall of systolic blood pressure of 10 mmHg or greater from the peak level with increasing exercise intensity; (f) diastolic blood pressure above 110 mmHg or systolic above 220 mmHg; (g) dizziness; (h) ataxic gait; and (i) pallor or cyanosis.

Training of personnel: Personnel assisting with the administration of screening treadmill tests will have BLS

certification and an experienced clinician will either conduct the test or be in the immediate vicinity (i.e., can be present within 3 minutes). A physician will interpret ECG and BP responses for all screening treadmill tests.

Screening of volunteers: To minimize risks of exercise testing in subjects, testing will be conducted only after the volunteer is examined by a clinician and after a resting ECG is obtained and evaluated. During exercise testing, the ECG is monitored constantly and BP is measured frequently. Exercise tests are terminated if any of the ACSM absolute or relative stopping criteria are met. The AHA-recommended emergency equipment and supplies will be available, including: automated electronic defibrillator; portable oxygen tank, nasal cannula, ventimask, non-rebreathing mask, and appropriate tubing to connect to the oxygen tank; oral airways; bag-valve-mask hand respirator; syringes and needles; IV tubing, solutions, and stand; and adhesive tape. The Exercise Research Laboratory operates as a 911 emergency response facility, as do all other UCH outpatient clinics.

Exercise training. The risks of exercise training will be minimized by the use of individualized exercise prescriptions and by having exercise professionals supervise the exercise training sessions.

Tissue Biopsies: Risks of the adipose and muscle biopsy procedures will be minimized by having a trained clinician perform the procedure. Persons with a prior history of allergies to local anesthetics will not be enrolled. Participants will return to the laboratory within one week of the biopsies to assess wound healing.

DXA: The acquisition of DXA data by trained research staff minimizes radiation exposure by reducing the need to perform repeated scans. Scans will not be performed in women who are pregnant.

Venipuncture: The risks of hematoma and infection are minimized by having trained personnel perform the procedures using sterile techniques.

Confidentiality and privacy: These risks will be minimized by not including personal identifying information on the forms, when possible, and by conducting interviews and collection of personal information in a private setting.

Evaluation of study-related events

Participants will meet with a study clinician every 4 weeks to review a Health Status Questionnaire that the participants will complete. The questionnaire queries about changes over the past 4 weeks in medications, health status, concerns with study medications or exercise. The clinician will specifically note on the form whether there are any concerns that are possibly, probably, or definitely related to the study. Participants will also be instructed to report concerns that may be study related when they occur to the research nurse practitioner, [name]. [name] will initiate event reports for both the programmed and spontaneous complaints.

